 $^{^{\}rm 6}$ PK blood samples obtained at 0h will be pre-dose samples on Days 4, 8 and 12

⁷ Pre-dose

⁹ Assessments on Study Days 1-3, 5-7, and 9-11 should be done pre-dose.

Table 8-2 Assessment schedule Part 2, Patients 1-16

Epoch	Scree	ning													Treatr	nent									
Study Phase	Screening	Baseline											Т	reatme	nt									Study Completion	30 Day safety follow up call
Visit Numbers ¹	V1	V2 ²	V3	V3.1	V3.2				V3.	3			V3.4	V3.5	V4 ³	V5	V6			\	/7			V777	n/a
Visit numbers (internal use only)	1	4	201	201.1	201.2	2			201.	.3			201.4	201.5	202	203	204			2	05			299	
Visit name (internal use only)	Screening	Day -1	Day 1	Day 2	Day 3			I	Day	4			Day 5	Day 6	Day 7	Day 14	Day 21			Da	y 28			End of study	
Study Day(s)	-28 to -4	-1	1	2	3				4				5	6	7	14	21			2	28			35	65
Study Day(s)	-20 10 -4	-1													-1 +1	-1 +1	-1 +1			-1	+0			-1 +2	
Time (post-dose)	-	0h	-			0h	1h	2h	3h	4h	8h	12h			-	-	-	0h	1h	2h	3h	4h	8h	-	
Informed consent	Х																								
Inclusion / Exclusion criteria	Х	х																							
Dose administration ⁴														Х											
Domicile								Χ																	
Medical history/current medical conditions	×																								
Demography	Х																								
Body height	Х																								
Body weight	Х																								
Hepatitis and HIV Screen	Х																								
Vital Signs	Х	Х	Х	Х	Х				Χ				Х	Х	Χ	Χ	Х	Х						Х	
Physical	Χ	Х																Х						Х	

Epoch	Scree	ning													Treatr	nent									
Study Phase	Screening												Т	reatme										Study Completion	30 Day safety follow up call
Visit Numbers ¹	V1	V2 ²	V3	V3.1	V3.2			,	V3.3	3			V3.4	V3.5	V4 ³	V5	V6			\	/7			V777	n/a
Visit numbers (internal use only)	1	4	201	201.1	201.2			2	201.	3			201.4	201.5	202	203	204			2	05			299	
Visit name (internal use only)	Screening	Day -1	Day 1	Day 2	Day 3			D	ay	4			Day 5	Day 6	Day 7	Day 14	Day 21			Da	y 28			End of study	
Study Day(s)	-28 to -4	-1	1	2	3				4				5	6	7	14	21				28			35	65
			-						-						-1 +1	-1 +1	-1 +1		1		+0	ı	1	-1 +2	
Time (post-dose)	-	0h	-			0h	1h	2h	3h	4h	8h	12h			-	-	-	0h	1h	2h	3h	4h	8h	-	
examination																				 	-	ļ			
Alcohol Test, Drug Screen, and Cotinine Test	Х																								
ECG evaluation	Х																							X	
Hematology	Х	Х														Х		Х						Х	
Blood chemistry ⁵	Х	Х	Х	Х	Х				Χ				Х	Х	Х	Х	Х	Х						Х	
Urinalysis	Х	Х	Х	Х	Х				Х				Х	Х	Х	Х	Х	Х						Х	
Corporate Confidential Information	Х	Х	Х	Х	х				Х				Х	х	Х	Х	Х	Х						х	

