		Х													Х			Х							
	×	Х	Х												Х	Х		x						Х	
	X	Х													Х			Х							

Epoch	Scree	ning														Treat	ment										
Study Phase	Screening	Baseline												Tr	reatme	nt										Study Completion	30 Day safety follow up call
Visit Numbers ¹	V1	V2 ²	V3	V3.1	V3.2				V3	.3				V3.4	V3.5	V4 ³	V5		V6			١	/7			V777	n/a
Visit numbers (internal use only)	1	4	201	201.1	201.2				201	1.3			2	201.4	201.5	202	203	2	204			2	05			299	
Visit name (internal use only)	Screening	Day -1	Day 1	Day 2	Day 3				Day	4				Day 5	Day 6	Day 7	Day 14		Day 21			Da	y 28			End of study	
Study Day(s)	-28 to -4	-1	1	2	3				4	ļ				5	6	7 -1 +1	14 -1 +1		21 1 +1				28 +0			35 -1 +2	65
Time (post-dose)	-	0h	-			0h	1h	2h	3h	41	n 8I	h 1:	2h			-	-		-	0h	1h	2h	3h	4h	8h	-	
PK blood collection ⁹						Х	Х	Х	Х	X	X		Х	Х		Х	Х		Х	Х	Х	Х	Х	Х	Х		
Adverse events															×												
Columbia-Suicide Severity Rating Scale	Х	Х															х			Х						X	
Concomitant Medication															Х												
Arterial spin labeling MRI ¹⁰		Х														Х											
Phase/Study completion information		Х																								Х	

¹ Visit structure given for internal programming purpose only

Information

² MRI can be done within 2 days prior to the baseline visit

³ MRI can be conducted within a day +/- of the Day 7 visit

⁴ Patient is expected to take the drug every day for 4 weeks. Corporate Confidential

Corporate Confidential Information

Table 8-3 Assessment Schedule, Part 2 Patients 17 to 72, approximately

Epoch	Scree	ning						Treatr	nent					
Study Phase	Screening	Baseline				Treat	ment						Study Completion	30 Day safety follow up call
Visit Numbers ¹	V1	V2 ²	V3	V4 ³	V5	V6			٧	7			V777	n/a
Visit numbers (internal use only)	1	4	201	202	203	204			2	05			299	
Visit name (internal use only)	Screening	Day -1	Day 1	Day 7	Day 14	Day 21			Da	y 28			End of study	
Study Day(a)	-28 to -4	4	1	7	14	21			2	8			35	65
Study Day(s)	-20 10 -4	-1	1	-1 +1	-1 +1	-1 +1			-1	+0			-1 +2	
Time (post-dose)	•	0h	•	-	-	-	0h	1h	2h	3h	4h	8h	-	
Informed consent	Х													
Inclusion / Exclusion criteria	X	Х												
Dose administration ⁴						×	(
Medical history/current medical conditions	Х													
Demography	X													
Body height	Х													
Body weight	Х													
Hepatitis and HIV Screen	Х													
Vital Signs	Х	Х	Х	Х	Х	Х	Х						Х	
Physical examination	Х	Х					Х						Х	
Alcohol Test, Drug Screen, and Cotinine Test	Х													
ECG evaluation	X												X	

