8.4.4 Laboratory evaluations

Clinically relevant deviations of laboratory test results occurring during or at completion of the study must be reported and discussed with Novartis personnel. The results should be evaluated for criteria defining an adverse event and reported as such if the criteria are met. Repeated evaluations are mandatory until normalization of the result(s) or until the change is no longer clinically relevant. In case of doubt, Novartis personnel should again be contacted.

A central laboratory will be used for analysis of all specimens collected. For the purposes of monitoring, a separate sample will be obtained for serum creatinine and dipstick urine testing at a local laboratory and those results will be entered into the eCRF. Details on the collection, shipment of samples and reporting of results by the central laboratory will be provided to investigators in the laboratory manual.

Hematology

Hemoglobin, hematocrit, red blood cell count, white blood cell count with differential and platelet count will be measured.

Clinical chemistry

Blood samples for clinical chemistry should be collected early morning after an overnight fast of at least 8 hours.

Sodium, potassium, creatinine, estimated GFR using the 4 variable MDRD study equation, cystatin C, urea, uric acid, chloride, albumin, calcium, phosphate, alkaline phosphatase, total bilirubin, GGT, AST, ALT, aPTT (activated partial thromboplastin time), PT/INR, CK, glucose, total cholesterol, triglycerides. If the total bilirubin concentration is increased above 1.5 times the upper limit of normal, direct and indirect reacting bilirubin should be differentiated.

In Part 1, LFTs (total bilirubin, AST, ALT, GGT, alkaline phosphatase) and coagulation tests (aPTT, PT/INR) will be included as part of the chemistry panel on screening, Days -1, 4, 8, 12, 14, and end of study visits.

Urinalysis

Urine samples for urinalysis,

Corporate Confidential Information

will be requested while they are at the clinic.

Urine test by dipstick e.g. Combur9: leucocytes, nitrite, pH, protein, glucose, ketones, urobilinogen, bilirubin, blood/hemoglobin

If the dipstick result is positive for protein, nitrite, leucocytes and/or blood, the sample will be sent for microscopic analysis of WBC, RBC and casts. If casts are noted, the type is to be specified on the relevant CRF page.

Corporate Confidential Information

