**Part 2 will enroll n=72 patients randomized 3:3:2 to LHW090**

Corporate Confidential Information

The study will be conducted in two parts. Part 1 will enroll a single cohort of 12 patients who will be randomized in a 2:1 ratio of LHW090 to placebo. An intra-patient dose escalation scheme will be employed starting at a [redacted] once daily dose for the first four day cycle, and then the dose will be escalated [redacted] once daily for the next four days and then [redacted] once daily for four days. If a renal event occurs during the treatment periods of the study or any of the individual stopping criteria are met, then dosing will be stopped for that individual patient. For the purposes of this study, a renal event will be defined as a reproducible increase from baseline serum creatinine of  $\geq 0.3$  mg/dL confirmed on a repeat measurement within 24-48 hours ([Mehta et al 2007](#), [Khwaja 2012](#)). Throughout the study, any serum creatinine assessment that is increased  $\geq 0.3$  mg/dL compared to baseline will trigger a repeat assessment of serum creatinine after 24 hours to confirm whether criterion for a renal event is met.

Corporate Confidential Information

Part 2 will be double-blind and placebo-controlled to assess the safety and tolerability of 2 dose levels of LHW090, [redacted] once daily for 4 weeks. Approximately 72 patients will be enrolled in Part 2 and randomized in a 3:3:2 ratio to LHW090

[redacted] and placebo. Therefore, in Part 2, approximately 27 patients are expected to be randomized to each of the active doses, and 18 patients are expected to be randomized to placebo. Randomization will be stratified by ARB dose (see Protocol) at the time of enrollment. Patients who meet the eligibility criteria at screening will have baseline assessments of renal function [redacted] collected on Day -1 prior to beginning the treatment phase on Day 1. Centrally-analyzed laboratory assessments performed at screening will be used to determine patient eligibility for the trial.

Corporate Confidential Information

The first 16 patients in Part 2 will be domiciled for the first 7 days of dosing to ensure careful monitoring of renal function and pharmacokinetic parameters. On Day 7 at the investigator's discretion, the patients will be released to complete the remaining 3 weeks of the treatment phase.

Corporate Confidential Information

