## **7 Statistical methods for safety and tolerability data**

### **7.1 Variables**

Corporate Confidential Information

Corporate Confidential Information

The primary safety variable will be the proportion of patients who develop a renal event. The two parts of the study will be analyzed separately. A renal event is defined as a reproducible increase in serum creatinine of  $\geq 0.3$  mg/dL from baseline confirmed on a repeat measurement within 24 to 48 hours.

Change from baseline for serum creatinine will be evaluated and categorized as  $< 0.3$  mg/dL and  $\geq 0.3$  mg/dL. The analysis will be based on central laboratory results. Baseline will be defined as the average of all available pre-dose measurements (excluding screening values).

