## 7.2 Statistical model, assumptions and hypotheses

For Part 2, no inferential analysis of renal events will be conducted due to only having 1 subject that fulfilled the criteria. A frequency table will be produced instead.

Historical data from internal Novartis studies in a similar patient population may be used to supplement the information from patients on placebo in the current study.

For each part, change from baseline for serum creatinine data will be analyzed using a linear mixed effects model for repeated measurements. The model will include treatment as a fixed effect, visit as a repeated effect, treatment by visit interaction and baseline as a continuous covariate. An unstructured covariance model will be used. Point estimates and the associated 95% confidence intervals for the difference between treatment and placebo at each visit will be provided.

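### Part 2 creatinine on Days 2-6 is scheduled for only 16 of about 72 patients; if the unstructured model covers those days with uncorrected standard errors, its 95% intervals there cover about 81-92%

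*SAP*

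**What the plan says.** SAP 7.2 analyses change from baseline in serum creatinine, separately for each part, with a repeated-measures model containing treatment, visit, their interaction and baseline. On the covariance it says "An unstructured covariance model will be used", and on the output "Point estimates and the associated 95% confidence intervals for the difference between treatment and placebo at each visit will be provided". Protocol 11.4.4 describes the same model as supportive. SAP 7.1 adds "The analysis will be based on central laboratory results".

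The Part 2 schedule differs between two groups of patients. SAP 1.4 states "The first 16 patients in Part 2 will be domiciled for the first 7 days of dosing". In Protocol section 8, "Table 8-2 Assessment schedule Part 2, Patients 1-16" lists blood chemistry on Days 1 to 7, 14, 21, 28 and 35, whereas "Table 8-3 Assessment Schedule, Part 2 Patients 17 to 72, approximately" lists it on Days 1, 7, 14, 21, 28 and 35 only. Creatinine belongs to that panel (Protocol 8.4.4: "Sodium, potassium, creatinine, estimated GFR using the 4 variable MDRD study equation").

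Neither SAP 7.2 nor Protocol 11.4.4 lists the visits in the model, separates the domiciled patients, or names a degrees-of-freedom method or small-sample correction. Protocol 11.4.3 leaves missing creatinine values to the model likelihood.

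**The concern.** Read literally, the Part 2 model has ten post-baseline visits, and five of them are observed in about 16 patients. The likelihood fills in Days 2-6 for the other 56 or so patients by regressing the early visits on the later ones, and that regression is estimated from the 16. Standard errors that treat the estimated covariance as known ignore the error in the regression. The fit converges and its output looks ordinary, so nothing would warn a reader.

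Days 2-6 fall in the period when patients were kept on site so that renal function could be watched. SAP 7.2 has also dropped inference on renal events, because only one subject met the definition, so this model is the only inferential renal comparison in the visible plan. Intervals that are too narrow on those days could turn chance into an early renal signal, or offer reassurance with false precision.

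**Working it through.** The documents give no coverage or precision figure for this model, so there is none to reproduce. The power statement in Protocol 11.6 concerns the renal-event proportion.

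**Inputs from the documents.** SAP 1.4: "approximately 27 patients are expected to be randomized to each of the active doses, and 18 patients are expected to be randomized to placebo". The first 16 patients have the fuller schedule (Tables 8-2 and 8-3).

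**Assumptions.** The 3:3:2 ratio holds within the first 16: 16 × 3/8 = 6, 16 × 3/8 = 6, 16 × 2/8 = 4. Errors are normal and nobody drops out. Between-visit correlation is varied, because the documents do not give it.

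**Parameter count.** Ten post-baseline visits (Days 2-7, 14, 21, 28, 35) give 10 × 11 / 2 = 55 covariance parameters. Within the 16 patients there are 16 − 3 = 13 degrees of freedom after arm means, and 13 − 5 = 8 after regression on the five later visits.

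**Mechanism.** Ignoring the baseline covariate, the model's early-visit arm mean is (early mean in the 16) + B × (late mean in all − late mean in the 16). REML divides the residual sum of squares of the early-on-late regression by 13, although only 8 degrees of freedom remain, and the standard error ignores the sampling error of B.

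Hand check at correlation 0, one dose versus placebo, in units of the residual variance:
- Base factor: 1/4 + 1/6 = 0.417.
- True variance: error in B adds (1/4 − 1/18 + 1/6 − 1/27) × 5/(13 − 5 − 1) = 0.324 × 0.714 = 0.231, giving 0.648.
- Model variance: 0.417 × 8/13 = 0.256, plus about 0.714 × (1/18 + 1/27) = 0.066, giving 0.323.
- Ratio of standard errors: √(0.648/0.323) ≈ 1.4.

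**Simulation.** REML fits of the SAP model with the baseline covariate, 1,200 runs per scenario, all converged. Days 2-6, each dose versus placebo, nominal 95%:

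| Between-visit correlation | Coverage, z | Coverage, t on 68 df | SD of estimate / mean model SE |
|---|---|---|---|
| 0 | 81.2% | 81.9% | 1.46 |
| 0.3 | 81.4% | 82.0% | 1.44 |
| 0.5 | 83.0% | 83.6% | 1.38 |
| 0.7 | 85.7% | 86.3% | 1.31 |
| 0.9 | 89.8% | 90.4% | 1.17 |
| Decaying with time | 81.2-83.4% | 81.9-84.0% | 1.40-1.47 |

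Pooled active versus placebo gives the same picture. Days 7-35 keep 94.6-94.9% (z) and 95.0-95.2% (t). If Day 1 also counts as post-baseline (11 visits, 500 runs), Day 2-6 coverage by z is 79.6%, 80.5% and 88.9% at correlations 0.3, 0.5 and 0.9.

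Separate simulations without the baseline covariate agree, reaching about 91% at correlation 0.9 and about 92% at 0.95. A per-visit analysis in the 16 patients covers about 95% throughout.

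**Corrections within one model, correlation 0.5.** Satterthwaite degrees of freedom with the unadjusted standard error give 84.9%. Kenward-Roger gives 90.4%.

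**Width relative to the uncorrected model interval** (no baseline covariate, t on 68 df):

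| Correlation | Needed for 95% coverage | Per-visit analysis of the 16 |
|---|---|---|
| 0.3 | about 1.5 | about 1.35 |
| 0.5 | about 1.4 | about 1.5 |
| 0.7 | about 1.3 | about 1.7 |
| 0.9 | about 1.2 | about 2.0 |

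**The case against.** The strongest reply is that the plan does not commit the error. SAP 7.2 names no standard-error method, so it has not chosen an uncorrected one, and nearby parts of SAP section 7 are redacted. Neither document lists the model's visits. Table 8-2 codes Days 2-6 as sub-visits V3.1 to V3.5, while all patients share V3 to V7 and V777, so a model on shared visits only would fit the text. This stands in part. A reader might infer that the reported Day 2-6 intervals are too narrow as a matter of fact, but the documents do not establish that. They promise an interval at each visit without excluding those days, and leave the method open.

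The size also depends on an unknown. The low end needs weak correlation, and at 0.95 the shortfall is only about 3 points. That too stands, though no correlation examined restored 95%.

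The reach is limited as well. The analysis is supportive, and no visible decision rule uses a Day 2-6 interval. Individual creatinine triggers, repeat tests and local-laboratory monitoring work without the model, and laboratory changes are also summarised by visit. A reader might infer that the renal safety conclusions as a whole are in doubt. They are not: Days 7-35 keep their coverage, and the renal-event frequency table does not use the model.

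Finally, discarding the later visits costs information when correlation is high. This is correct and belongs with the cost of the fix.

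**Conclusion.** The point holds conditionally. With Days 2-6 in the Part 2 model and uncorrected standard errors, the nominal 95% intervals on those days cover about 81-91% for between-visit correlations of 0 to 0.9, and about 92% at 0.95. Per-visit error is then about 8-19% (100 − 92 to 100 − 81) instead of 5%. This rests on a 6:6:4 split, normal errors and full data in the 16 patients; dropout among them was not simulated and would leave fewer patients at these visits.

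It is more than a missing detail, because the usual correction does not rescue the single model: Kenward-Roger reaches only about 90% at correlation 0.5. A reader might also take the wider per-visit interval to be the true width of the model's interval. It is not: calibration needs about 1.2-1.5 times, and any excess over that at higher correlation is information given up.

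**What to change.** In SAP 7.2, for Part 2:

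- Fit the unstructured model only to the post-baseline visits all patients share: Days 7, 14, 21, 28 and 35. That leaves 5 × 6 / 2 = 15 covariance parameters.
- For Days 2-6, report a per-visit ANCOVA with treatment and baseline in the domiciled patients. Use t intervals on its own residual degrees of freedom (16 − 3 − 1 = 12 with complete data) and label the results n=16.
- State the standard-error and degrees-of-freedom method for the model that remains.

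If a single model is kept with a Kenward-Roger correction, describe it as a partial remedy and not as equivalent to the split.

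The cost is SAP wording and one extra table, with no new data. Day 2-6 intervals become about 1.35-2.0 times as wide as the uncorrected model's over correlations 0.3 to 0.9. At 0.5 or below, little or no precision is lost against a calibrated model interval. At 0.9 the per-visit interval is about 2.0/1.2 ≈ 1.7 times as wide as a calibrated one, and that difference is lost borrowed information.

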### 7.2.1 Model checking procedures

For the frequency table of the proportion of patients with a renal events, patients who complete at least 2 weeks of treatment will be included in the denominator.

Corporate Confidential Information

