3.1 Study design

Part 1 will be enrolled as a cohort of 12 subjects (2:1 LHW090 and placebo). Patients will be domiciled from Day -2 to Day 14.

Corporate Confidential Information

Part 2 First 16 patients will be domiciled for 1 week, from day -2 to Dav 7. Rest of the dosing will be done off site.

Part 2 will enroll n=72 patients randomized 3:3:2 to LHW090 and placebo.

Corporate Confidential Information

This is a randomized, double-blind, parallel group, placebo-controlled study, in two sequential parts to evaluate the renal safety, tolerability and pharmacokinetics of LHW090 in patients with moderately impaired renal function. Patients aged 40 to 85 (inclusive) with an estimated glomerular filtration rate (eGFR) between 30 and 59 mL/min/1.73m² at screening (inclusive) on a stable dose of an angiotensin receptor blocker (ARB) will be considered for this study.

The study will be conducted in two parts. Part 1 will enroll a single cohort of 12 patients who will be randomized in a 2:1 ratio of LHW090 to placebo. An intra-patient dose escalation scheme will be employed starting at a daily dose for the first four day cycle, and then the dose will be escalated once daily for the next four days and then once daily for four days. If a renal event occurs during the treatment periods of the study or any of the individual stopping criteria are met, then dosing will be stopped for that individual patient. For the purposes of this study, a renal event will be defined as a reproducible increase from baseline serum creatinine of ≥ 0.3 mg/dL confirmed on a repeat measurement within 24-48 hours (Mehta et al 2007, Khwaja 2012). Throughout the study, any serum creatinine assessment that is increased ≥ 0.3 mg/dL compared to baseline will trigger a repeat assessment of serum creatinine after 24 hours to confirm whether criterion for a renal event is met.

function Corporate Confidential Information will be performed Starting on Day 1, the patient will begin treatment with study drug or placebo, and dose will escalate two times for a total dosing period of 12 days. Pharmacokinetic assessments will be collected as shown in the assessment schedule. After completing dosing, patients will be monitored for an additional 48 hours after which they will be discharged at the discretion of the investigator. The patient will be asked to return to the site approximately one week later for end of study assessments.

Corporate Confidential Information

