Study treatment must be discontinued and the patient withdrawn from the study if the patient withdraws consent. Patients may voluntarily withdraw from the study for any reason at any time. They may be considered withdrawn if they state an intention to withdraw, fail to return for visits, or become lost to follow-up for any other reason. If a patient withdrawal occurs for any reason, the Investigator must make every effort to determine the primary reason for a patient's withdrawal from the study and record this information on the CRF.

The Investigator should discontinue study treatment for a given patient or withdraw the patient from study if on balance they believe that continuation would be detrimental to the patient's well-being. Under the following circumstances, individual study treatment must be discontinued and the patient monitored until resolution of the reason for discontinuation according to the Investigator's discretion:

- A reproducible and persistent (confirmed on repeat assessment within 24 48 hr) increase
 in serum creatinine ≥0.3 mg/dL from baseline. Any increases in serum creatinine
 ≥0.3 mg/dL based on local laboratory assessments should trigger repeat assessments of
 serum creatinine until event resolution (e.g. serum creatinine within 10% of baseline) or
 event stabilization. Baseline is defined as the average of all available pre-dose
 measurements.
- Systolic blood pressure <90 mm Hg (must be confirmed on repeat measurement after 30 minutes) or symptomatic hypotension
- Any protocol deviation (e.g. use of an ACE inhibitor) that results in a significant risk to the patient's safety

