11.1 Analysis sets

For all analysis sets, subjects will be analyzed according to the study treatment(s) received.

The safety analysis set will include all subjects that received any study drug.

The PK analysis set will include all subjects with available PK data and no protocol deviations with relevant impact on PK data.

The PD analysis set will include all subjects with available PD data and no protocol deviations with relevant impact on PD data.

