11.4 Analysis of the primary variable(s)

11.4.1 **Variable(s)**

The primary safety variable will be the proportion of patients who develop a renal event. The two parts of the study will be analyzed separately. A renal event is defined as a reproducible increase in serum creatinine of ≥ 0.3 mg/dL from baseline confirmed on a repeat measurement within 24 to 48 hours. This threshold in serum creatinine was selected based on the published definitions of acute kidney injury (Mehta et al 2007, Khwaja 2012). Change from baseline will be evaluated and categorized as < 0.3 mg/dL and ≥ 0.3 mg/dL. The analysis will be based on central laboratory results. Baseline will be defined as the average of all available pre-dose measurements.

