11.4.3 Handling of missing values/censoring/discontinuations

For the analysis of the proportion of patients with a renal events described in Section 11.4.3, patients who complete at least 2 weeks of treatment will be included in the denominator. For the analysis of change from baseline in serum creatinine described in Section 11.4.4, all available data will be included and missing data will not be imputed (it will be estimated from the likelihood of the repeated measures model). Patients discontinued by the investigator due to a doubling of serum creatinine from baseline (based on local measurements) will be counted as having a renal event in the primary analysis regardless of the availability of a central serum creatinine value. In case more than 10% of patients drop out before 2 weeks, a sensitivity analysis using multiple imputation techniques may be considered.

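### The Part 2 renal-event proportion is based on 2-week completers, although a confirmed renal event itself stops treatment, so an early event short of a doubling can drop out of the primary result

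*SAP*

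**What the plan says.** **Denominator.** SAP 7.2.1, under a heading about model checking, states for the renal-event frequency table that "patients who complete at least 2 weeks of treatment will be included in the denominator". Protocol 11.4.3 set the same rule for the planned primary analysis.

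**Event.** Protocol 11.4.1 and SAP 7.1 define a renal event as a creatinine rise of at least 0.3 mg/dL from baseline, confirmed on a repeat within 24 to 48 hours. "The analysis will be based on central laboratory results."

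**Stop.** Protocol 7.1 lists a confirmed rise of the same size, with the same confirmation window, among the circumstances in which "individual study treatment must be discontinued and the patient monitored until resolution of the reason for discontinuation". Protocol 3.1 has a matching rule at the level of the single patient: "renal event occurs during the treatment periods of the study or any of the individual stopping criteria are met, then dosing will be stopped".

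**Exceptions visible in the protocol.** Under 11.4.3, "Patients discontinued by the investigator due to a doubling of serum creatinine from baseline", judged on local measurements, are counted as having an event even without a central value. The same section adds: "In case more than 10% of patients drop out before 2 weeks, a sensitivity analysis using multiple imputation techniques may be considered." Neither provision appears in the visible SAP text.

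**Current status.** SAP 7.2 drops the inferential analysis of renal events because only 1 subject met the criteria, and replaces it with a frequency table.

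**The concern.** The endpoint and the stopping criterion share a threshold and a confirmation window. Whether a patient reaches two weeks of treatment therefore depends partly on whether the event has already happened. A denominator restricted to those who reach two weeks conditions on the outcome, and does so where it matters most: a patient whose creatinine rises in the first days of dosing.

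This is the primary result of a renal safety study. Protocol 3.1 keeps the first 16 Part 2 patients in the unit for the first 7 days so that renal function can be watched closely. A confirmed rise found in that week is what the trial looks for, yet the rule can keep it out of the proportion that the trial reports.

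**Working it through.** The plan gives no figure for the effect of this rule. Its only relevant number is the count of 1 in SAP 7.2.

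**1. Can an early event be found and stopped before week 2?** Blood chemistry is scheduled daily on Days 1 to 7 and then on Days 14, 21 and 28 for the first 16 patients (Protocol Table 8-2). For the others it is on Days 1, 7, 14, 21 and 28 (Table 8-3). The Day 7 visit has a window of one day either side, so Day 6 to 8. Confirmation 1 to 2 days later falls on Day 7 to 10, before Day 14. A patient stopped then cannot have completed two weeks.

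**2. Are stop and endpoint the same measurement?** Not quite. For monitoring, "a separate sample will be obtained for serum creatinine and dipstick urine testing at a local laboratory", while the endpoint uses central results. A central event might not be matched by a local one, in which case the patient could continue and stay in the denominator. An early event therefore generally, but not always, removes the patient.

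**3. How far does the doubling exception reach?** A doubling needs a rise equal to baseline. Inverting the MDRD equation in Protocol 4.1:

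Scr = [175 × Age^(−0.203) × (0.742 if female) × (1.212 if African American) / eGFR]^(1/1.154)

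- Lowest eligible value (eGFR 59, age 85, female, without the 1.212 factor): 0.91 mg/dL.
- Highest (eGFR 30, age 40, male, with the factor): 2.85 mg/dL.

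A doubling is thus a rise of 0.91 to 2.85 mg/dL, about 3.0 to 9.5 times the 0.3 mg/dL that stops treatment. Rises in between are not covered. The protocol also does not say whether patients counted under this exception join the denominator.

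**4. When is imputation considered?** 10% of 72 is 7.2, so up to 7 early leavers trigger nothing. From 8 on it is optional.

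**5. Effect on the table.** Assume the planned sizes of 27, 27 and 18 (Protocol 3.1), and that the one event was early and excluded. Exact two-sided 95% upper limits: for no events, 1 − 0.025^(1/n); for one event, the p that solves (1−p)^n + n·p·(1−p)^(n−1) = 0.025.

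| Group holding the event | Event kept | Upper limit | Event dropped | Upper limit |
|---|---|---|---|---|
| One dose arm | 1/27 = 3.7% | 19.0% | 0/26 | 13.2% |
| Pooled active | 1/54 = 1.9% | 9.9% | 0/53 | 6.7% |
| Placebo | 1/18 = 5.6% | 27.3% | 0/17 | 19.5% |

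If the event were kept in the numerator while the patient left the denominator, a dose arm would show 1/26 = 3.8%. The text does not settle which of these applies.

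**6. Direction.** If instead the event was late and, say, 3 other patients in that arm left before week 2, the rule gives 1/24 = 4.2% against 1/27 = 3.7% of all treated. The rule can move the rate either way; only the loss of an early event is driven by the outcome.

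**The case against.** The exclusion is inferred. Neither document says that only completers enter the denominator, and neither says how the numerator treats an early event. Redacted text follows the SAP sentence directly and may contain an exception. Both points stand, and limit the claim to the natural reading of the visible text. They do not remove it: Protocol 11.4.3 writes out an exception for a doubling, which would hardly be needed if every early event were counted anyway.

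The live effect is also small. One subject qualified, the SAP already states this openly, and no test will be run. Early rises remain visible in the summaries of change below and above 0.3 mg/dL, in the repeated-measures model and in the laboratory listings. This stands too, but none of those outputs corrects the primary proportion.

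A reader might go further in three ways that the documents do not support.

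- That the observed event has been removed from the table. Its arm and day are not given, nor is the population in which it was counted.
- That the rule costs the planned comparison a definite amount of power. The share of events before week 2 is not given, any figure taken from the visit schedule depends on arbitrary choices, and SAP 7.2 has dropped the test.
- That all dosed patients must become the main denominator. That is a trade-off: it counts patients who left after brief exposure as non-events, which lowers the rate in a safety study.

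**Conclusion.** The concern holds on the natural reading. As written, the rule lets the outcome decide who enters the primary proportion, for confirmed rises from 0.3 mg/dL up to a doubling that stop treatment before week 2.

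Its size is bounded by the count in SAP 7.2: at most one event in a descriptive table. In a renal safety study, one event and none are nevertheless different primary results. The limits shown assume planned arm sizes and an early event; actual sizes, arm and day are not given. The conclusion also assumes that the redacted SAP text holds no further exception. The stopping rule itself is not in question.

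**What to change.** In the Part 2 frequency table:

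- Define the main denominator as the 2-week completers plus every patient with a centrally confirmed renal event, whatever the treatment duration, and count each such patient in the numerator as well. The event definition stays as it is.
- Carry the protocol's doubling rule into the SAP, and state that patients counted under it are also in the denominator.
- Add a row with the proportion among all treated patients. This needs one definition of the safety set. Protocol 11.1 says "The safety analysis set will include all subjects that received any study drug", whereas SAP 4 also requires no protocol deviation with relevant impact on safety, and SAP Table 4-1 excludes subjects assessed before written consent. The two should be reconciled first.
- State whether the 1 subject in SAP 7.2 is included under the present completer rule.
- Record that the change was made after the event count was known.

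The cost is a few sentences in the SAP and one rerun of a table, with no new data. The all-treated row counts early non-renal dropouts as non-events, which is why it is an addition and not the main row.
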